2.2. Treatment groups

Treatment groups considered for the analyses are S42909 50 mg b.i.d, S42909 100 mg b.i.d, S42909 200 mg b.i.d, S42909 400 mg b.i.d, S42909 600 mg and placebo corresponding to S42909 100 mg per day, S42909 200 mg per day, S42909 400 mg per day, S42909 800 mg per day, S42909 1200 mg per day and placebo.

They correspond to the randomised treatment over the W000-W006 period except for safety analyses for which treatment taken at inclusion visit is considered.

In the unlikely event of a patient has taken an incorrect Therapeutic Unit (TU) at a particular post-W000 visit in the double-blind treatment period, which would result in a switch of treatment group, the patient will be considered in the treatment group corresponding to their TU(s) taken until the switch. Their data recorded from the switch will be kept in the analyses. However, all safety data and IMP administration data of the patients with a switch of treatment group will be listed separately.

3. STATISTICAL METHODS

3.1. General considerations

3.1.1. Descriptive statistics

For **qualitative data**, the number of observed values, the number and the percentage of patients per class will be presented. Unless otherwise specified in the Tables, Listings and Graphs (TLG), no class "Missing" is considered.

For **quantitative data**, the number of observed values, the mean, the standard deviation, the median, the first and third quartiles, the minimum and the maximum will be presented.

For **event**, the following will be presented :

- Number of patients having experienced the event (n).
- Number of events that occurred (for AE analyses only) (NAE).
- Number of patients at risk for the event (N).
- Global incidence rate (%) calculated as the ratio between the number of patients having experienced the event and the number of patients at risk at the beginning of the study.

3.1.2. General definitions

The following definitions will be considered:

- **IMP** is the treatment intake (S42909 or Placebo) post randomisation.
- **Analysable value** will be defined as any non-missing value.
- **Baseline value** will be defined as the last analysable value prior to the first IMP intake (*i.e.* before or the same date as the first IMP intake date).
Note: In case of patient included and/or randomised but not treated (*i.e.* patients with treatment duration equal to 0): value at baseline is defined as the last analysable value prior or equal to the date of the inclusion visit.
- **Post-baseline value** will be defined as any value recorded at a given timepoint after baseline.
- **Change from baseline** will be defined as the arithmetic difference between a post-baseline value and the baseline value for a given variable at a given time point.
- **Relative change from baseline** will be defined as : $100 * \text{change from baseline} / \text{baseline value}$.

For safety criteria (except for adverse events), the following definitions will be applied:

- A value is considered under treatment if the assessment date is between the first IMP intake date (excluded) over the W000 and W006 period and the last IMP intake date "+ 15 days" (included).

Note: for all definitions concerning value under treatment '+ 15 days' was calculated according to the half-life of the S42909.

- High emergent abnormal value under treatment according to the laboratory reference ranges is defined as value \leq ULN (Upper Limit of Normal laboratory reference range) or missing at baseline and $>$ ULN under treatment.
- Low emergent abnormal value under treatment according to the laboratory reference ranges is defined as value \geq LLN (Lower Limit of Normal laboratory reference range) or missing at baseline and $<$ LLN under treatment.

- High emergent abnormal value under treatment according to the cut-offs for PCSA (Potentially Clinically Significant Abnormal value) values is defined as value \leq ULS (Upper Limit used to define potentially clinically Significant abnormal values) or missing at baseline and $>$ ULS under treatment.
- Low emergent abnormal value under treatment according to the cut-offs for PCSA values is defined as value \geq LLS (Lower Limit used to define potentially clinically Significant abnormal values) or missing at baseline and $<$ LLS under treatment.

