After repeated oral administration of S42909, steady-state is reached by Day 4, with no accumulation of the parent drug after 10 days of repeated administration of S42909 at 600, 1200 and 1800 mg (with standard meals). Food intake (High Fat High Calorie (HFHC) or standard breakfast) increases Cmax and exposure for S42909 and S45015. S45236 C_{max} and exposure are decreased at 600 mg after a HFHC breakfast.

Results of one combined study (PKH-42909-003) investigating the S42909 drug-drug interactions with a CYP2C9 substrate (warfarin) and with a CYP3A4 substrate (midazolam) showed that S42909 at the dose of 210 mg q.d does not interact with the elimination of warfarin or midazolam, in accordance with circulating concentrations much lower than K_i and supporting a low risk of drug-drug interaction with S42909.

Safety data in clinical studies

Overall, 278 subjects have been enrolled into the S42909 clinical studies; out of these, 203 have received at least one administration of S42909.

S42909 was administered in doses ranging from:

- 105 mg to 840 mg in oral single dose administration and 210 mg to 630 mg in oral repeated dose administration for periods between 5 and up to 14 days, in the Gelucire® 44/14 formulation (currently discontinued),
- 600 mg/day to 2100 mg/day in single oral dose administration and repeated dose administration with the newly developed formulation for 10 days.

Overall, S42909 was well tolerated up to the dose of 1800 mg in oral single dose and 1200 mg in oral repeated dose administration. There were no clinically relevant abnormalities concerning biologic and hematologic parameters, physical examination, vital signs or on ECG tracings.

The majority of the reported Treatment Related Emergent Adverse Events were mild or moderate, mainly diarrhoea probably due to the laxative effect of main excipient a cellulosic derivative.

During the conduct of the CL1-42909-013 dose-escalation study, diarrheic episodes were reported in several subjects starting from the daily dose of 1200 mg of S42909. The episodes increased in frequency, duration and severity when escalating the dose and at the same dose when passing from single dose administration to repeated dose administration. Typically, the episodes were mild to moderate in intensity occurring rapidly after study drug intake and resolved spontaneously the same day.

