(13) In fasting condition for 10 hours.

(14) Four PK samples will be taken at W000, W004 and W006 visits and one predose PK sample will be taken at W001, W002 visits in all participants. The participants who agreed to participate in the optional PK analysis in participating centres will have 9 PK samples collected over 12 hours at W000 visit and 13 PK samples collected over 24 hours at W004 visit instead of the 4 PK samples and will be assigned to a dose group by the IWRS.

(15) Before the IMP intake and after specific consent collected for these optional samplings.

(16) β -HCG, FSH, biochemistry, HbA1c (if a result from previous 3 months is not available), haematology, urinalysis and ECG prescribed at ASSE visit: they should be collected within the 5 calendar days prior to W000 visit, with the results available to be checked at W000 visit (at the latest) before randomisation.

(17) INR to be followed at each visit (or more often if judged necessary by the investigator) if patient is under anticoagulant therapy with warfarin or phenprocoumon.

The maximum total volume of blood collected per participant during the study will be around 304 ml for the mandatory study and around 410 ml in case of optional pharmacokinetic analysis, genomic and non genomic biomarkers sampling.

Table (4.2.2) 2 - Pharmacokinetic Investigation Schedule

Time relative to the first administration on the visit day	Pre-dose	0h	1h	2h	3h	End of visit ⁽²⁾	4h	5h	6h	8h	12h ⁽⁴⁾	13h	14h	15h	24h
IMP intake at the end of the meal		X									X				
PK Blood sampling for all participants: W000, W004, W006 ⁽³⁾	X ⁽¹⁾		X		X	X									
PK Blood sampling for all participants: W001, W002	X ⁽¹⁾														
PK Blood sampling over 12-hours for participants having agreed to this optional PK analysis: W000	X ⁽¹⁾		X	X	X	NA	X	X	X	X	X ⁽¹⁾				
PK Blood sampling over 24-hours for participants having agreed to this optional PK analysis: W004	X ⁽¹⁾		X	X	X	NA	X	X	X	X	X ⁽¹⁾	X ⁽⁵⁾	X ⁽⁵⁾	X ⁽⁵⁾	X ^{(1),(5)}

(1) PK sampling before meal and IMP administration.

(2) Blood sampling will be performed in all patients at the end of the study visit, just before leaving or at T4h if possible.

(3) Except at W000 and W004 for patients participating to the optional PK blood sampling over 12 hours and 24 hours respectively.

(4) Could be adjusted to a maximum of 2 hours before, to accommodate a more convenient dinner time.

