6.3. Previous and concomitant treatments

The previous treatments will be recorded within the 6 months prior to the selection for treatment involved in the studied disease and within the 6 weeks prior to the selection for other treatments.

The following treatments will be forbidden because they are known to interact significantly with wound healing or may interact with the IMP treatment:

- Topical corticosteroid application on and around the ulcer within 15 days prior to selection and during the study
- Oral corticosteroids within the month prior to selection and during the study
- Immunomodulators, immunosuppressants, cytotoxic chemotherapy within the month prior to selection and during the study
- Pentoxyfylline within the month prior to selection and during the study
- Acetylsalicylic acid treatment started within the last 6 weeks prior to the selection or during the study. Acetylsalicylic acid is allowed at antiaggregant dose and at long term \leq 350 mg daily (coronary disease).
- Drugs known to be BCRP substrates during the study such as methotrexate, mitoxantrone, irinotecan, imatinib, lapatinib, topotecan, rosuvastatin, sulfasalazine.
- Oral anticoagulant treatments known to be BCRP substrates such as acenocoumarol, fluindione, apixaban, rivaroxaban. Anticoagulant if prescribed during the study.
- Venoactive drugs within the month prior to selection and during the study
- Participants on oral or parenteral antibiotic therapy. Long-term, low dose prophylactic antibiotic therapy started at least one month before the selection is however acceptable if there is no change in the treatment during the study.
- Local antibiotic therapy on the surface of RU, during the study.

- Oral and parenteral antibiotherapy during the study, except if less than or equal to 7 days.
- NSAIDs on long-term chronic treatment within one month prior to the selection, except if taken less than one week within the last month. NSAIDs are not allowed during the study except if taken once and not longer than 3 consecutive days.

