- Haematology (within the 5 calendar days prior to W000 with results available at W000 at the latest, W001, W002, W004, W006 and W008 visits): haemoglobin, haematocrit, red blood cells, MCV, MCH, MCHC, platelets, white blood cells, lymphocytes, monocytes, eosinophils, basophils and neutrophils (white blood cells, lymphocytes, monocytes, eosinophils, basophils and neutrophils must be assayed in absolute value and entered in the e-CRF in this unit). For patients under warfarin or phenprocoumon, International Normalized Ratio (INR) will be performed at each visit (including W003) or more often if judged necessary by the investigator.

- Standard urinalysis will be performed using a dipstick, within the 5 calendar days prior to W000 with results available at W000 at the latest, W004, W006 and W008 visits by the investigator or a delegated person. Urinalysis: pH, proteins, blood, leucocytes, bilirubin, ketones bodies, nitrites and glucose.
- A blood sampling will be performed for β -HCG or FSH analysis (within the 5 calendar days prior to W000 visit, with results available at W000 visit at the latest) to diagnose pregnancy and menopause respectively. β -HCG tests will be repeated at W004 and W008 visits for women of child-bearing potential. Depending on the local regulation, pregnancy tests can be additionally repeated throughout the treatment period (urinary tests which is not to be entered into e-CRF).

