3.6.2. Clinical laboratory evaluation

For all parameters, the **dosing of samples come from local laboratories**. So no quantitative analysis will be performed. In the qualitative analysis, data will be compared to reference ranges provided by these local laboratories.

Definition:

- A laboratory value is considered as analysable if non-missing and not flagged in the ClinTrial database as "not analysable".

Analyses:

For each biochemical and haematological parameter, the following analyses will be performed:

- Number and percentage of patients with at least one high/low emergent abnormal value under treatment, according to the laboratory reference ranges and to the cut-offs for PCSA values.

- Laboratory parameters classified (number and percentage of patients in each class) according to these reference ranges and cut-offs, and using shift tables from baseline to the worst (high and/or low) values under treatment.

Moreover, listings of patients with out-of-range or PCSA analysable values emergent under treatment and of non-analysable values excluded from analyses will be provided.

Urinary parameters will be described in classes (absent, trace, +, ++, +++, +++) at baseline and at each post-baseline visit under treatment.

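### In patients whose baseline INR is already above the ULN, the SAP's reference-range rule can never count a further rise as emergent, and the SAP gives no INR cut-off or change from baseline to make up for it

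*SAP*

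**What the plan says.** **Who has INR measured.** Footnote 17 to the investigation schedule (Protocol 4.2.2) has INR followed at each visit "if patient is under anticoagulant therapy with warfarin or phenprocoumon". Protocol 8.2 lists it under haematology and says that, for patients on those two drugs, "International Normalized Ratio (INR) will be performed at each visit (including W003) or more often if judged necessary by the investigator". The forbidden treatments in Protocol 6.3 include "Anticoagulant if prescribed during the study", so monitored patients should already be anticoagulated at entry.

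**How a high value becomes emergent.** SAP 3.1.2 has two parallel rules.
- Reference range: "High emergent abnormal value under treatment according to the laboratory reference ranges is defined as value" at or below ULN, or missing, at baseline and above ULN under treatment.
- PCSA: "High emergent abnormal value under treatment according to the cut-offs for PCSA (Potentially Clinically Significant Abnormal value) values is defined as value" at or below the upper PCSA limit (ULS), or missing, at baseline and above ULS under treatment.

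**What is reported.** For each biochemical and haematological parameter, SAP 3.6.2 gives "Number and percentage of patients with at least one high/low emergent abnormal value under treatment, according to the laboratory reference ranges" and also by the PCSA cut-offs. It adds shift tables from baseline to the worst value on both sets of classes. Its listings of abnormal values are limited to emergent ones, and it rules out quantitative laboratory analysis because the laboratories are local. Protocol 10.1.4 had planned the value at each visit, the last value under treatment and the change from baseline to that last value. The SAP text does not name INR and gives no PCSA limits.

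**Interaction evidence.** Protocol section 2 reports that "S42909 at the dose of 210 mg q.d does not interact with the elimination of warfarin or midazolam". This trial gives 100 to 1200 mg per day.

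**The concern.** An emergence rule built on the normal range suits tests that should start normal. INR in this trial is measured only where it is raised on purpose. For these patients the baseline condition of the reference-range rule is expected to fail from the start, so the count cannot respond to what happens on treatment.

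At stake is how the INR output is read. The trial collects INR at every visit in placebo and five dose groups, three of which (400, 800 and 1200 mg per day) exceed the daily dose of the warfarin interaction study. The documents report no interaction study with phenprocoumon. A low or zero count of emergent high INR would naturally be read as reassurance, when it may only reflect the rule.

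**Working it through.** The plan states no figure to reproduce. The check applies the two rules to example values.

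**Inputs.** The rules come from SAP 3.1.2. The documents do not give an INR ULN or ULS, so these are assumptions: ULN 1.2, and ULS 1.5, 2, 3, 4 or 5.

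**Formula.** For a limit L (ULN or ULS), baseline B and on-treatment value T:

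emergent(L) = (B ≤ L or B missing) and (T > L).

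If B > ULN, the first bracket is false, so emergent(ULN) is false for every T.

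| INR, baseline to on-treatment | Reference-range rule (ULN 1.2) | PCSA rule counts it if ULS is | PCSA rule misses it if ULS is |
|---|---|---|---|
| 2.5 to 3.5 | no | 3 | 1.5, 2, 4, 5 |
| 2.5 to 4.5 | no | 3, 4 | 1.5, 2, 5 |
| 2.5 to 6.0 | no | 3, 4, 5 | 1.5, 2 |
| 3.2 to 6.0 | no | 4, 5 | 1.5, 2, 3 |
| 2.1 to 2.9 | no | none of the five | 1.5, 2, 3, 4, 5 |
| 1.1 to 4.5 | yes | 1.5, 2, 3, 4 | 5 |
| missing to 4.5 | yes | 1.5, 2, 3, 4 | 5 |

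The PCSA rule works for an anticoagulated patient only when B ≤ ULS < T. The shift tables use the same limits as class boundaries. A rise that crosses no boundary stays in its row's own class: high to high on the reference range, and unchanged on the PCSA classes.

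**Other laboratory output.** A non-emergent rise does not enter the abnormal-value listings, and there is no summary of values or changes in which it could appear.

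**Dose comparison.** By day, 1200 / 210 = 5.7. By intake, the top dose is 600 mg twice daily, so 600 / 210 = 2.9.

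**Number of patients.** The documents do not say how many take warfarin or phenprocoumon. If 5% to 15% of the 121 included do (an assumption), that is 0.05 × 121 = 6 to 0.15 × 121 = 18. With equal allocation, five sixths of them, about 5 to 15, would be on S42909, or about 1 to 3 per arm.

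**The case against.** A reader might infer that an INR rise caused by the drug cannot be counted anywhere, so that the tables must show none. The documents do not support that.

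- **The PCSA rule and PCSA shift classes are a second route.** With a suitable cut-off they would catch a rise from 2.5 to 4.5 or 6.0. Table templates and further safety definitions sit in separate documents, so a workable INR limit may exist. This stands. However, the route is unspecified here, and one threshold still misses a smaller consistent shift.
- **Adverse events are a third route.** Protocol 8.2 asks for clinically significant laboratory abnormalities to be recorded as adverse events, and SAP 3.6.1 tabulates treatment-emergent events. This stands for marked rises. It depends on the investigator's judgement and gives neither the size of the change nor a denominator of monitored patients. Protocol 8.3.1.1 also excludes expected local reactions at the ulcer, naming bleeding, from adverse event reporting.
- **Not every countable case is an artefact.** A normal baseline rising to 4.5 is counted and may be real.
- **The exposure argument has limits.** The ratio of 5.7 is by day and falls to 2.9 per intake. No passage compares absorption between the formulations. The more than proportional exposure of the parent drug comes from single fasting doses in healthy young men, and one metabolite with high exposure, S45236, rose less than proportionally. Protocol section 2 also cites circulating concentrations far below the inhibition constant.
- **No study objective names an anticoagulant interaction.** INR may be there for individual monitoring. That does not make an uninformative summary useful, but it limits how much weight the point carries.

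**Conclusion.** The point holds in a bounded form. For a patient whose baseline INR exceeds ULN, the reference-range rule counts 0% of further rises, whatever their size. This follows from the rule itself. That monitored patients will usually be in this position is an expectation, based on their anticoagulation and an assumed ULN of about 1.2. Whether the PCSA output makes up for it cannot be settled from the documents.

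The laboratory analysis could therefore look falsely reassuring for INR, although it is not shown to be blind to every rise. The loss is sharper because the SAP removed the value and change-from-baseline description in Protocol 10.1.4. The reason given, local laboratories, was already part of Protocol 8.2, and a patient's change against his or her own baseline depends less on the local range than a class count does. The primary and secondary efficacy analyses are unaffected. The number of patients concerned is unknown; 6 to 18 is only an illustration.

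**What to change.** Change SAP 3.6.2 for INR only:

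1. Do not rely on the reference-range emergence rule for this test.
2. In the INR-monitored patients, describe INR at baseline and at each visit, with change from and ratio to baseline for the last and the maximum on-treatment value, for placebo, each dose and S42909 pooled. Show the number of monitored patients in each group.
3. List all their INR values, emergent or not, alongside recorded anticoagulant changes and bleeding adverse events.
4. State the INR PCSA cut-off if one exists, or say that there is none.

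The cost is some SAP wording, one table and one listing, mainly from data already collected. With perhaps 1 to 3 patients per arm under the assumption above, the result will be descriptive and cannot establish or exclude an interaction. The change concerns reporting only and implies nothing about dosing or anticoagulant management.

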3.2. Disposition and baseline characteristics

Disposition of patients and baseline characteristics will be described by randomised treatment group, to assess their comparability, and overall (treatment groups pooled).

Details concerning definitions on the disposition of patients and baseline characteristics are provided in Appendix 5.2. and provided in the Specifications document.

3.2.1. Disposition of patients

Disposition of patients, including reasons for withdrawal, will be summarized during the study by randomised treatment, overall and by visit, in the RS).

3.2.2. Protocol deviations

Protocol deviations before or at inclusion (W000), as well as after inclusion on W000-W004, W000-W006 and W000-W008 periods, will be described in the RS, by category of important deviations (*based on ICH E3 guideline and ICH E3 Q&A*).

If necessary a listing of non-included randomised patients will be provided.

3.2.3. Demographic data and other baseline characteristics

Demographic data and other baseline characteristics such as life habits, history of the venous leg ulcers, venous duplex scan results, compression stocking dispensing(at W000 and at each visit), ankle brachial pressure index, baseline value of efficacy criteria (ulcer assessments and pain intensity), vital signs and ECG parameters at baseline will be described in the RS.

The main patients' characteristics will also be described in the FAS and the PPS.

The QTcF interval at baseline will be also described in classes (\leq 450,]450; 480],]480; 500] and $>$ 500ms, in accordance with ICH E14 guideline) and the following continuous data will also be described in classes:

Age ([18 ; 64], [65; 84], \geq 85 years).

All previous treatments for venous leg ulcers will be described in the RS, by Anatomical Therapeutic Chemical (ATC) code. All medical history other than venous leg ulcers and surgical or medical procedures history, will be described in the RS by primary system organ class (SOC) and preferred term (PT).

For compression stocking, compliance on W000-W004 and W000-W006 period will be also described in classes ($<$ 80, [80; 120], and $>$ 120%).

Details concerning this compliance are provided in Appendix 5.2.

